16.4 MAINTENANCE PHASE

At the completion of Phase I, the weight loss intervention groups will be cluster randomized to a Skills Based Maintenance Program or a Motivation Based Maintenance Program for Phase II: Months 7-18. During Phase II, participants in both maintenance programs will attend group sessions every two weeks, although a few individual sessions will be offered at selected points in the maintenance program (replacing the group session). Both maintenance programs will have individual sessions at the same point in the maintenance program, although different content will be offered to the two conditions. Intervention sessions for each maintenance program are outlined in detail in the intervention manual (counselor manual). (Please see Lifestyle and Behavior Change Program Manual)

CHAPTER 17

SERIOUS ADVERSE EVENTS/PROCEDURES

17.0 SERIOUS ADVERSE EVENTS/PROCEDURES

17.1 DEFINITION

A serious adverse event (SAE) is defined as any adverse experience, occurring to a PRIDE participant during the course of the study that results in any of the following outcomes: Death, a life-threatening adverse experience, inpatient hospitalization or prolongation of existing hospitalization, a persistent or significant disability/incapacity, or a congenital anomaly/birth defect. Important medical events that may not result in death, be life-threatening, or require inpatient hospitalization may be considered a serious experience when, based upon appropriate medical judgment, they may jeopardize the patient or participant and may require medical or surgical intervention to prevent one of the outcomes listed in this definition.

NOTE: Any overnight hospital stay is an SAE.

In addition to the Serious Adverse Events described above, we would like to document *outpatient* procedures or surgeries pertaining to the abdomen or pelvic region. Please use the Serious Adverse Events form to document procedures such as the following:

- Bladder suspension through an incision in the vagina (tension-free vaginal tape {TVT} or trans-obturator tape {TOT})
- Laparoscopic bladder suspension (laparoscopic Burch)
- Laparoscopy for pelvic surgery (involving ovary, fallopian tubes, uterus including hysterectomy, etc.)
- Laparoscopy for abdominal surgery (gall bladder)
- Cystoscopy (examination of interior of bladder)
- Hysteroscopy (examination of interior of uterus) and /or D & C
- Repair of vaginal prolapse (anterior colporrhophy or cystocele repair, sacrospinous ligament suspension and/or urethral plication or Kelly plication)

Events that occur during screening need not be reported to the Coordinating Center. Only events that occur between the date of randomization and the date of the final visit should be documented.

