5.0 STUDY POPULATION

5.1 SAMPLE SIZE

Of the 330 volunteers for PRIDE, the first 100 women who agree to participate in the Urodynamic Study will be enrolled (approximately 50 at each of 2 clinical centers).

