9.0 SERIOUS ADVERSE EVENTS

The risk of urodynamics testing is minimal. Serious adverse events as defined by the US Food and Drug Administration (death, a life-threatening event, inpatient hospitalization or prolongation of hospitalization, a persistent or significant disability or incapacity) will be routinely ascertained in this trial. Important medical events may be considered serious adverse experiences by the clinical site investigator if the event might jeopardize the participant or might require medical or surgical intervention to prevent one of the outcomes defined as serious.

Safety-related events will be reported in a timely fashion as required by the Data and Safety Monitoring Board and the IRB.

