4.3.4 Baseline Urodynamic Study

The initial urodynamic study visit (UDS) must take place after SV2 and before the RV.

4.3.5 Follow-up Visits at Months 6, 12, and 18

Target dates for the follow-up visits will be based on the individual's randomization date:

6-month visit: Target date is 26 weeks after RV; window is 24-28 weeks

12-month visit: Target date is 52 weeks after RV; window is 50-54 weeks

18-month visit: Target date is 78 weeks after RV; window is 76-80 weeks

4.3.6 6-Month UDS

6-month UDS: Target date is 26 weeks after RV; window is 24-28 weeks

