Appendix 11A: Calibration Log

Appendix 11B: Standard Annotations for UDS

Appendix 11C: Classification & Examples of Flow Patterns in the Non-Invasive UroFlow Study

11.0 URODYNAMIC SUBSTUDY

11.1 OVERVIEW PHYSICAL EXAMINATION & URODYNAMIC (UDS) TESTING

Equipment used for physical examination and urodynamic (UDS) testing in PRIDE will be the same equipment used in the Urinary Incontinence treatment Network (UITN) study. Procedures are similar also but the data recorded may be different in PRIDE and the instructions should be reviewed carefully before measurements begin.

A volunteer subgroup of 100 women in PRIDE will undergo a standardized pelvic floor evaluation and urodynamic studies at baseline and at 6 months to elucidate the mechanism by which weight loss improves incontinence. The UDS investigators will conduct exploratory analyses to evaluate whether baseline urodynamic measures such as intravesical pressures, Valsalva leak point pressures, and detrusor instability can identify women who are most likely to experience improved continence after weight reduction. They will also investigate the mechanism by which weight loss improves continence by examining the relationship of improvement in continence and changes in urodynamic measures.

The examination will consist of a physical examination (includes Pubococcygeus Contraction Assessment, Pelvic Organ Prolapse Quantification Exam (POP-Q) and the Q-Tip Test) and urodynamic testing (includes cough stress test, non-instrumented uroflow (NIF), post-void residual urine volume (PVR) and cystometric evaluation). All measures will be performed at baseline (before randomization) and at 6 months post randomization.

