17.2 REPORTING SERIOUS ADVERSE EVENTS (SAEs)

17.2.1 Lag Time to Report

The Investigator must notify the Coordinating Center as soon as possible by telephone if any serious or unexpected adverse event occurs in any participant *after the participant has been randomized*. The SERIOUS ADVERSE EVENT FORM should be completed and faxed to the Coordinating Center the same week that the event is reported.

All such reportable events must be monitored until the condition subsides and/or the cause is identified. Updates to the SAE form can be made, if new information becomes available, by posting a query to the website and then making an addition or change to the form.

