17.2.3 Reporting Responsibilities

The Coordinating Center is responsible for notifying both the sponsor (NIDDK) and the Data and Safety Monitoring Board of all serious adverse events. The Principal Investigator is responsible for notifying the site's local IRB according to institutional guidelines.

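### Serious adverse events that start between the baseline urodynamic examination and randomisation are not required to reach the Coordinating Center, and through it NIDDK and the DSMB

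*Protocol*

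**What the plan says.** Three parts of Chapter 17 of the Operations Manual set the central reporting rule.

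- 17.1 first exempts screening: "Events that occur during screening need not be reported to the Coordinating Center". It then limits the record itself: "Only events that occur between the date of randomization and the date of the final visit should be documented".
- 17.2.1 gives the investigator a duty to notify the Coordinating Center of an event that arises "after the participant has been randomized".
- 17.2.3 sets the onward route: "The Coordinating Center is responsible for notifying both the sponsor (NIDDK) and the Data and Safety Monitoring Board of all serious adverse events".

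The timing of the sub-study examination is fixed elsewhere. Section 4.3.4: "The initial urodynamic study visit (UDS) must take place after SV2 and before the RV". Section 11.1: "All measures will be performed at baseline (before randomization) and at 6 months post randomization".

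The urodynamic sub-study protocol takes a wider view of safety reporting. Its section 9.0 lists the serious adverse event categories and says that they "will be routinely ascertained in this trial", with reporting as the DSMB and the IRB require. Its section 6.1 sends any serious adverse event during the trial to each IRB. Neither section limits this to the time after randomisation, and Chapter 17 makes no exception for the sub-study.

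**The concern.** The usual reason for not collecting serious adverse events before randomisation is that no study procedure could yet have caused them. That reason does not apply here. Before randomisation, sub-study women undergo bladder catheterisation and retrograde filling, a swab placed in the urethra, and cystometry with bladder and rectal catheters (sub-study protocol 7.3). All of this is done for research under a separate consent. The main protocol itself describes the tests as invasive when it explains why only a subset has them (8.3.3).

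The days just after a procedure are when an acute complication would most be expected. For the baseline examination, those days fall before randomisation unless the two visits are very close together. The body charged with participant safety is then not assured of hearing about such an event, although the sub-study protocol says that these events are routinely ascertained. A woman who is not randomised because of a complication is the clearest case. Centrally she would appear only as an ineligible candidate with one main reason marked (10.7), and the criteria in Appendix 12A have no item for a complication of a study procedure.

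**Working it through.** The documents give no figure to reproduce. The check compares the reporting window with the visit sequence and then counts examinations.

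**Step 1: which events the rule covers.** The sequence is Screening Visit 2, baseline urodynamic visit, Randomization Visit, month-6 urodynamic visit (24 to 28 weeks after randomisation, 4.3.6), final visit. Chapter 17 classifies by when the event occurs, not by when its cause did.

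| Onset of event | Required to reach the Coordinating Center? |
|---|---|
| After the baseline examination, before randomisation, woman later randomised | No |
| After the baseline examination, woman never randomised | No |
| After randomisation, whatever the cause | Yes |
| After the month-6 examination, up to the final visit | Yes |

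**Step 2: how many examinations are followed by an uncovered interval.** Inputs: 100 women (sub-study protocol 5.1: "the first 100 women who agree to participate in the Urodynamic Study will be enrolled") and 2 examinations each (11.1).

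- Planned: 100 × 2 = 200 examinations, of which 100 precede randomisation; 100 / 200 = 50%.
- With a proportion L lost by month 6, the share is 100 / (100 + 100 × (1 − L)).
- L = 5% (retention expected in 9.5): 100 / 195 = 51.3%.
- L = 28/336 = 8.3% (DSMB Guidelines, Appendix III): 100 / 191.7 = 52.2%.
- L = 10% (sample size assumption in 12.2.1): 100 / 190 = 52.6%.
- L = 15% (retention limit in DSMB Guidelines, Appendix II): 100 / 185 = 54.1%.

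These loss rates are for the whole trial. Applying them to the sub-study is an assumption.

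**Step 3: how long the interval is.** Section 10.6 says that the Randomization Visit should fall within 4 weeks of Screening Visit 2. The baseline urodynamic visit comes after Screening Visit 2, so on that target the interval is under 4 weeks. Section 4.3 removes the limits between individual visits but caps the time from the eligibility interview to randomisation at 9 months. The 9 months also contain the earlier screening steps, so the interval must be shorter than that.

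**Step 4: what it could cost in information (illustration only).** If no events are seen in n examinations, the exact one-sided 95% upper limit on the risk per examination is 1 − 0.05^(1/n). This is 2.95% for n = 100 and 1.49% for n = 200. The documents give no event rate. For assumed risks of 0.5%, 1% and 2%, the chance of seeing at least one event, 1 − (1 − p)^n, is 39%, 63% and 87% in 100 examinations, against 63%, 87% and 98% in 200. Both calculations treat examinations as independent. They also take the extreme case in which every event after a baseline examination starts before randomisation, so they show the most that the gap could cost.

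**The case against.** The strongest case on the other side has four parts.

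- **The gap is bounded.** The cut-off is the date of the event, so a complication of the baseline examination that starts after randomisation is reportable. On the 10.6 target the interval is under 4 weeks. This stands, with the qualification that the target is advisory and 4.3 imposes no limit between visits.
- **Other oversight exists.** The sub-study protocol requires IRB reporting (6.1) and reporting as the DSMB and IRB require (9.0). This stands as to the IRB. It does not close the gap to the DSMB, because Chapter 17 is the operating instruction and its only stated route to the DSMB runs through the Coordinating Center. One could try to reconcile the texts by taking the trial to begin at randomisation. But section 9.0 of the sub-study protocol opens with the risk of urodynamic testing, and half of that testing comes before randomisation.
- **The rule is permissive.** 17.1 says that screening events need not be reported, which does not forbid a report. This is true, but the next sentence confines documentation to the period from randomisation.
- **The stakes are modest.** The risk is described as minimal, and no endpoint, sample size or between-arm comparison changes. This stands. It affects the priority of the point, not whether the texts agree.

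A reader might go further than the documents allow in three ways. One might infer that these events can never reach the DSMB, or that it would judge the procedure on the month-6 examinations alone. Neither follows, because post-randomisation events after a baseline examination are reported and a voluntary report is possible. One might read 50% as the share of events missed. It is a share of examinations, and the documents give no basis for a share of events. One might conclude that a woman who is not randomised falls under no reporting duty at all. The IRB statement in 6.1 still applies; what is missing is the Chapter 17 route to the Coordinating Center.

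**Conclusion.** The point holds as an inconsistency with a limited but real safety consequence. Chapter 17 as written leaves out serious adverse events that start between the baseline urodynamic examination and randomisation, including those in women who are then not randomised. The sub-study protocol makes promises that Chapter 17 does not carry out. The uncovered interval follows about 100 of 200 planned examinations (50%, or 51% to 54% with 5% to 15% loss by month 6). For women who are randomised, it should last under 4 weeks if the 10.6 target is kept.

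This rests on reading Chapter 17 literally and on the planned sub-study size. Few events are expected, and the efficacy results are not at risk. The point merits an amendment because a statement of minimal risk is best supported by counting events after every examination, and because the document itself fixes the window that prevents this.

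**What to change.** Reconcile 17.1 and 17.2.1 with sections 6.1 and 9.0 of the sub-study protocol. State that, for women in the urodynamic sub-study, serious adverse events are documented and reported to the Coordinating Center from the start of the baseline urodynamic visit, whether or not the woman is later randomised. Make this an explicit exception to the sentence in 17.1 on screening events. The amendment should also say until when a woman who is not randomised is followed for this purpose, since the documents give no end point for her.

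Use the existing Serious Adverse Event form. Tabulate these events separately from post-randomisation events, so that the between-arm safety comparison is unchanged. The cost is about one sentence in each of the two sections and a few extra reports.

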17.2 REPORTING SERIOUS ADVERSE EVENTS (SAEs)

17.2.1 Lag Time to Report

The Investigator must notify the Coordinating Center as soon as possible by telephone if any serious or unexpected adverse event occurs in any participant *after the participant has been randomized*. The SERIOUS ADVERSE EVENT FORM should be completed and faxed to the Coordinating Center the same week that the event is reported.

All such reportable events must be monitored until the condition subsides and/or the cause is identified. Updates to the SAE form can be made, if new information becomes available, by posting a query to the website and then making an addition or change to the form.

17.2.2 Records Requested

Surgical reports and discharge summaries for pelvic and abdominal procedures performed in the hospital should be requested. All other SAEs will be self-reported. Any records obtained by the site in order to complete the SAE data form should be filed in the participant's chart at the site. Do not send copies of hospital records to the Coordinating Center unless specifically requested.

17.2.3 Reporting Responsibilities

The Coordinating Center is responsible for notifying both the sponsor (NIDDK) and the Data and Safety Monitoring Board of all serious adverse events. The Principal Investigator is responsible for notifying the site's local IRB according to institutional guidelines.

17.2.4 Filling Out the SAE Form

Complete the banner information and enter the date of the visit if the participant is reporting the event in person. Alternately, enter the date you receive enough information about the event to warrant a report. Choose the visit bubble that is closest to the date of the event.

Please work through the form carefully and enter as much information and as many dates as you are able. Note that question 1 can have multiple responses.

If the participant has had an *outpatient* procedure pertaining to the abdomen or pelvic region, mark the bubble for hospitalization and enter the date of

the procedure in **both** the “Date hospitalized” and the “Date discharged” boxes.

Question 3: Enter the diagnosis. Remember to use all capitals, be brief and try to obtain the correct medical diagnosis. If no diagnosis is available enter the main symptom experienced by the participant. If appropriate, include the cause of the event (e.g. “Hysterectomy due to excessive vaginal bleeding”). The terms you enter for “Diagnosis” will be reproduced verbatim on data listings and reports so please be precise and concise.

Question 4: Choose the one response that best describes the participant’s condition at the time you are filing this report. If the outcome does not fall into any of the categories provided, mark “Other” and enter a very brief description of outcome. Do not write outside the boxes because the data will not be accepted to the database.

Question 5: Please indicate whether or not the participant will continue in the study. If the participant will no longer continue to be followed, please fill out a Termination Report.

Question 6: Treatment administered: please mark all that apply.

Question 7: Is event related to the intervention? Please choose one response only.

Question 8. Use these boxes to provide additional helpful information. Again, please be brief, one letter per box, all capitals, don’t write beyond the boxes.

It can be difficult to describe life events on a form! Please call the Coordinating Center if you are uncertain about completing any parts of this form.

CHAPTER 18

DATA SYSTEM AND MANAGEMENT

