13.6.4 Concurrent Medications and Serious Adverse Events

Ask the participant if she has seen her doctor, been hospitalized or experienced any serious health events in the past six months. Any events that meet the definition of "Serious Adverse Event" (SAE), described in Chapter 17 of the PRIDE Operations Manual, must be reported to your IRB and documented on the SAE Form. Please note that SAEs should be reported as soon as you are made aware of them. This follow-up visit provides an additional occasion to check for events that may have happened to participants you haven't seen frequently. The responses to questions 1 and 2 on the Cost Analysis form may be a cue to probe further for SAEs as well, however, these questions relate only to the past three months. Please review all self-administered questionnaires before the participant leaves the site. If you are uncertain whether a medical visit or health event qualifies as an SAE, please contact the Coordinating Center for advice.

Ask the participant if she has had any changes in prescription medications, or

started or stopped medications. Check to see if she has started or stopped over-the-counter medications also. The participant should bring to the visit all prescription and non-prescription medications that she takes on a regular basis. Look at each medication and record either the trade name (preferably) or the generic name of each medication, but not both. Record over-the-counter medications only if they are taken on a regular basis.

Please record all medications even if there has been no change since the previous visit.

If the participant is not taking any medications regularly, print "NONE" in the boxes after "1. Trade Name."

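### Outpatient procedures are coded as hospitalizations on the SAE form with no rule keeping them out of SAE counts, and the visit question's fixed six-month look-back leaves time uncovered after a late or missed visit

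*Protocol*

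**What the plan says.** **Coding of procedures.** Section 17.1 defines an SAE by outcome, inpatient hospitalization among them, and adds "NOTE: Any overnight hospital stay is an SAE". A separate paragraph then opens "In addition to the Serious Adverse Events described above, we would like to document" and lists outpatient abdominal and pelvic procedures, to be recorded on the same SAE form. Section 17.2.4 tells staff, for such a procedure, to "mark the bubble for hospitalization and enter the date of" the procedure in both the "Date hospitalized” and the “Date discharged” boxes".

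**Reporting.** Section 17.2.3: "The Coordinating Center is responsible for notifying both the sponsor (NIDDK) and the Data and Safety Monitoring Board of all serious adverse events". The investigator informs the local IRB under institutional rules.

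**Visit question.** Sections 13.3.3 (Month 6) and 13.6.4 (Month 12) have staff ask whether the participant has seen her doctor, "been hospitalized or experienced any serious health events in the past six months". Section 13.7 carries the Month 12 procedures over to Month 18. The Cost Analysis form, offered as a further cue, reaches back three months.

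**Period to be covered.** Section 17.1: "Only events that occur between the date of randomization and the date of the final visit should be documented". Section 4.3.5 sets the visit windows, for example "12-month visit: Target date is 52 weeks after RV; window is 50-54 weeks".

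**The concern.** The two instructions on procedures do not fit together. Section 17.1 places the listed outpatient procedures outside the SAE definition as such; section 17.2.4 gives each of them a seriousness code. Anyone who tabulates the hospitalization item as recorded counts events that need not be serious.

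The visit question has the opposite weakness. The reporting period runs unbroken from randomization to the final visit, but the question covers a fixed six months whatever the time since the woman was last seen.

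What is at stake is the safety tabulation. Section 10.0 says only serious events are routinely ascertained. Under Appendix 3B the DSMB's closed report compares SAEs between groups, and Appendix II lets the board alter or stop the study on evidence of serious harm. Apart from pelvic and abdominal procedures done in hospital, for which records are requested, SAEs are self-reported (17.2.2).

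**Working it through.** There is no figure in the plan to reproduce. The first part is a comparison of text, the second is interval arithmetic.

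**1. Coding.**
- Status under 17.1: recorded in addition to SAEs, so not an SAE by being on the list.
- Entry under 17.2.4: hospitalization marked, with the same date for admission and discharge.
- What separates the record afterwards: the identical dates, and the diagnosis text in Question 3, which 17.2.4 says is reproduced verbatim in listings and reports.
- Stated rule for using those two items: none in the document.
- Identical dates alone are not a clean marker, because a same-day admission that is serious for another reason would carry them too. The procedure name is also needed.

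The documents give no procedure rate. As an assumption for scale only, if 2% to 5% of 330 women had a listed procedure, that is 0.02 × 330 = 6.6 to 0.05 × 330 = 16.5, or about 7 to 17 records coded as hospitalizations. Some of these could be serious on medical judgment.

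**2. Look-back.** Inputs from section 4.3.5, in weeks after randomization: Month 6, 24–28 (target 26); Month 12, 50–54 (target 52); Month 18, 76–80 (target 78). Six months is taken as 26 weeks, the spacing of the targets; using 183 days instead (26.14 weeks) changes results by about 0.1 week.

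Shortest interval = earliest later visit − latest earlier visit. Longest interval = latest later visit − earliest earlier visit. Uncovered time = interval − 26, or 0 if negative.

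| Consecutive attended visits | Interval (weeks) | Uncovered, range | Uncovered, on target |
|---|---|---|---|
| Randomization to Month 6 | 24 to 28 | 0 to 2 | 0 |
| Month 6 to Month 12 | 50−28 = 22 to 54−24 = 30 | 0 to 4 | 0 |
| Month 12 to Month 18 | 76−54 = 22 to 80−50 = 30 | 0 to 4 | 0 |
| Month 6 to Month 18 (12 missed) | 76−28 = 48 to 80−24 = 56 | 22 to 30 | 26 |
| Randomization to Month 12 (6 missed) | 50 to 54 | 24 to 28 | 26 |
| Randomization to Month 18 (both missed) | 76 to 80 | 50 to 54 | 52 |

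Section 4.3 describes the windows as optimal, so later visits are possible. Section 13.10 lets a woman who dropped out rejoin and resume visits, with no change to the question.

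A question about the time since the last completed visit, or since randomization, leaves 0 weeks uncovered for every pattern in the table.

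**The case against.** **Procedures.** The records are separable: same-day dates mark them off from an overnight stay, and the named procedure appears in every listing. The DSMB decides the content and format of its own reports (Appendix 3B), so a sensible tabulation may have been adopted. A reader might infer that these records go to NIDDK, the DSMB and the IRBs as SAEs. The document does not say so: 17.2.3 speaks of SAEs, and 17.1 sets the procedures beside them. This stands. What remains is a code that contradicts the definition, and no stated rule that corrects for it.

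**Look-back.** The visit question is a back-up. Sections 13.3.3 and 13.6.4 require SAEs to be reported as soon as the site knows of them and call the visit an extra occasion to check. Section 13.8 has women asked to report any hospitalization and suggests interim calls, especially to the education group. Events in the gap remain reportable. This also stands, and it limits the claim to a risk of missing events. But the back-up is meant for women seen infrequently, and controls have seven sessions in 18 months (16.2) against 24 group visits in the first 26 weeks and two-weekly sessions afterwards (16.3, 16.4).

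**Masking of harm.** A reader might go further and infer that the errors hide an excess in the weight-loss arm, since the list includes incontinence operations and controls have fewer contacts. The documents do not support this. Extra incontinence procedures would raise control counts, while missed events would lower them. Participants also agree not to start new incontinence treatment, surgery included (section 6.2, criterion 9), and the list covers unrelated surgery such as gall bladder laparoscopy. Nor are SAEs the only safety information: blood pressure and the Beck inventory are collected at 6, 12 and 18 months (section 8.1).

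**Conclusion.** The point holds as two defects in the SAE collection rules that can miscount SAEs. Certain miscounting in both directions is not shown.

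- A hospitalization code is placed on procedures that 17.1 lists apart from SAEs. Over-counting follows only if the item is tabulated without using the dates and the diagnosis; nothing in the document requires their use. The number affected cannot be derived from the documents.
- The six-month question leaves at most 2 weeks uncovered before Month 6 and 4 weeks between later in-window visits, and nothing when visits fall on target. The material gap is about 22 to 30 weeks after one missed visit. This rests on taking six months as 26 weeks and on the question being asked as written.

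The size and direction of any between-arm effect are unknown. The matter concerns safety tabulation only; the primary efficacy analysis is untouched. Correction is worthwhile because it costs little and the SAE comparison informs the DSMB.

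**What to change.** 1. **Section 17.2.4.** Instruct staff not to mark hospitalization for an outpatient procedure unless a seriousness criterion in 17.1 is met. Keep the actual diagnosis or procedure in Question 3, because that text is what listings reproduce, and enter OUTPATIENT PROCEDURE in Question 8 or in a dedicated field. For forms already received, have the Coordinating Center tabulate records of listed procedures with identical admission and discharge dates separately from SAEs, unless another seriousness criterion applies.
2. **Sections 13.3.3 and 13.6.4, and Month 18 by reference.** Replace the six-month look-back with *since your last completed study visit (or randomization)*, and have staff state that date to the participant.

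The cost is two wording changes in the manual, one extra tabulation rule, and slightly longer recall for women who missed a visit. Any automatic query that expects a seriousness item to be filled would need adjusting so that these forms do not trigger it.
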